#### **Analytic Methods**

The analysis of the data will be conducted by the Statistical Package for the Social Sciences, IBM SPSS 28 and R Studio.

RCT 1 the antenatal period: Provide the evidence as to whether an intervention to support mothers who are suffering from anxiety or depression during the antenatal period will make a significant difference to these mothers viz a viz the parents in the control group

Baseline characteristics will be compared between the two groups (Intervention/Control) to observe whether the two groups showed any demographic differences. To assess baseline participant differences, binominal logistic regression will be used to test for demographic differences across the two study groups – the intervention group and the control group. Any baseline demographic factor that differed between the two groups at p < 0.10 will be included as a potentially confounding variable in follow-up models testing for the effect of the intervention. Effect sizes will be given in terms of odds ratios for analyses using binomial logistic regression, , with 1 meaning no difference, values under 1 meaning less likely, and values over 1 meaning more likely to occur in the intervention compared to control group. However, this approach will be feasible if there is enough detail to conduct such analysis for certain demographic variables. If such problem arises, alternatively, a Chi-Square test of association will be carried out by selected demographic variables to see whether the two groups showed any demographic differences. The null hypothesis specifies that there is no association between the two variables and will be accepted if the p-value exceeds the 0.05 level of significance. The effect size for the chi-square test was measured using Cramer's V.

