Pre-and post-means, medians, and standard deviations for all the measures, namely the GAD-7, EPDS and R-DAS will be compared and analysed between the respective groups, namely for the intervention and control group participants. Descriptive measures will also be presented visually using boxplots comparing pre-and post- test scores for each group. The paired samples t-test can be used to compare the mean scores of the pre-and post-sessions of both groups. If the differences of the pre-post measures deviate from the normality assumption, the Wilcoxon Signed-Ranks test should then be used to compare the scores between the pre-post periods for both intervention and control groups. The change of the pre- and post-test scores can be categorized into three groups as no change, lower

post-test score and higher post-test score and compared through the Chi-Square test between intervention and control to assess whether the increase or decrease in the post-test score is differing among the two groups.

Next, to assess the effect of the study condition, there are three adequate ways to analyse a numerical outcome (GAD-7, EPDS and R-DAS) where the common point of these approaches is that the prescores must be considered (the best approach will be chosen accordingly):

- 1. Independent samples-test on change of scores (i.e., the post-minus-pre differences), assuming the normality assumption is satisfied. The overall test is statistically significant if it yields a sufficiently small p-value. Following the hypothesis testing, the Cohen's d effect size statistic will be calculated for intervention effects. If a nonparametric approach is chosen (assuming normality assumption is deviated), the Mann-Whitney test should be performed on change scores. The effect size for the Mann-Whitney U test is calculated by dividing the standardised test statistic z and square root of the number of pairs n.
- 2. Two-way mixed-model ANOVA with group as between-subjects factor (intervention and control groups) and time-point as within-subject factor (i.e., repeated measures; with two levels, baseline, and post-intervention). Note that the p-value for interaction in this design will be equivalent to the p-value from the independent samples t-test on change scores mentioned in (1). This will also answer the essential question of the study: do the changes from baseline differ between the groups?

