- 3. Analysis of covariance (ANCOVA) of post-intervention scores with baseline score as the covariate. This approach differs subtly from the two mentioned above. Analysis of covariance treats the pre-test value as a covariate that can be a source of variation that may influence post-test scores, and accordingly the post-test score is regressed on both the pre-test score and the grouping variable. ANCOVA adjusts the pre-test scores, increasing the power to determine whether or not there has been a treatment effect. This approach tests the null hypothesis of no difference between the control and treatment post.

Should the results indicate that there has been significant improvement at post-testing, one should also evaluate for any differences in the change of scores between the two groups through stepwise linear regression using a bootstrapping procedure with 5000 replications recommended for analyses with smaller sample sizes (Preacher and Hayes, 2008). Groups alone will be included in Model 1, and any confounds that differed across the two groups at baseline will be included in Model 2, allowing for the comparison of the effect size as a function of study condition in unadjusted and adjusted models. Results will be determined to be statistically significant if p values were <0.05.

Furthermore, it would be of interest to see whether there is an association between a high score in ANRQ and the incidence of depression and anxiety. Thus, the idea is to check for any possible correlation between ANRQ and EPDS and ANRQ and GAD-7 for both pre- and post-testing, through the Pearson correlation or alternatively the Spearman correlation, if the assumption of normality is not satisfied.

The assumption of normality to perform all the above tests will be evaluated by the Shapiro-Francia test. If the assumption of normality has been violated, the p-value will be less than 0.05. If the assumption of normality has not been violated, the p-value will be greater than 0.05. This is because the Shapiro-Wilk test is evaluating the null hypothesis that the distribution of the data is equal to a normal distribution. Rejecting the null hypothesis means that the distribution of the data is not equal to a normal distribution.

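### The only covariate-adjusted between-group model is run only after an undefined "significant improvement", so the adjusted estimate promised elsewhere would be reported selectively

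*Protocol*

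**What the plan says.** All of this is in the protocol's Analytic Methods section.

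- **Baseline factors.** After the baseline comparison: "Any baseline demographic factor that differed between the two groups at p < 0.10 will be included as a potentially confounding variable". This concerns the later models for the intervention effect, and no condition is attached.
- **Within-arm tests.** "The paired samples t-test can be used to compare the mean scores of the pre-and post-sessions of both groups", with the Wilcoxon signed-ranks test as the fallback.
- **Between-arm analyses.** The text continues that "to assess the effect of the study condition, there are three adequate ways to analyse a numerical outcome": a test on change scores, a mixed ANOVA, or ANCOVA with the baseline score as covariate. No condition is attached here either. Of the mixed ANOVA it says: "This will also answer the essential question of the study: do the changes from baseline differ between the groups".
- **The conditional step.** After the three analyses: "Should the results indicate that there has been significant improvement at post-testing, one should also evaluate for any differences in the change of scores". This is a comparison of the arms by stepwise regression with 5000 bootstrap replications. Model 1 holds group alone, and "any confounds that differed across the two groups at baseline will be included in Model 2". The stated purpose is "allowing for the comparison of the effect size as a function of study condition in unadjusted and adjusted models".

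**The concern.** The commitment to adjust for imbalanced baseline factors is unconditional, but the only model that carries it out is conditional. The condition is also not operational. It could refer to the paired tests within arms or to the between-arm analyses, and it does not say which of the three outcomes, or which arm, must improve.

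Each reading has its own defect. Under a between-arm gate, the adjusted estimate appears only when the unadjusted difference happened to be large, so it is missing from null and borderline results and too large when shown. Under a within-arm gate, the condition says little about treatment, because mothers enter on high EPDS or GAD-7 scores, which tend to fall on re-measurement in either arm.

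With 60 mothers, chance imbalance is plausible and Model 2 is the plan's stated answer to it. Readers of a null or borderline result would not see whether adjustment changes the conclusion.

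**Working it through.** **Inputs from the protocol.** 30 mothers per arm (Trial Design; Trial Flow Chart). Significance at p < 0.05 (Analytic Methods), taken as two-sided because sidedness is not stated. Entry follows a raised EPDS or GAD-7 score (Inclusion Criteria).

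**Assumed inputs.** The protocol gives no effect size, standard deviation, pre-post correlation or power, so it has no figure of its own to reproduce. I assume true standardised differences d of 0.3, 0.5 and 0.8; one prespecified covariate correlated 0.4 with the outcome; selection of the top 15% or 30% of scores; and pre-post correlations r of 0.6 to 0.9.

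**Reading 1: the gate is a significant between-arm improvement.**

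The gate opens when the two-sample t statistic exceeds 2.002 (58 degrees of freedom). The noncentrality is d × √(30/2) = 3.873 d.

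| True d | Noncentrality | Gate opens | Adjusted estimate missing |
|---|---|---|---|
| 0.3 | 1.16 | 20.7% | 79% |
| 0.5 | 1.94 | 47.8% | 52% |
| 0.8 | 3.10 | 86.1% | 14% |

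The size of the adjusted estimate was simulated (200,000 trials per d). The outcome is d × group + 0.4 × covariate + noise, scaled to total SD 1 within arm. The gate is the unadjusted t-test; the estimate is the group coefficient with the covariate in the model.

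| True d | Mean adjusted estimate, always reported | Mean when the gate opens | Ratio to truth |
|---|---|---|---|
| 0.3 | 0.300 | 0.595 | 0.595 / 0.3 = 1.98 |
| 0.5 | 0.501 | 0.678 | 0.678 / 0.5 = 1.36 |
| 0.8 | 0.800 | 0.855 | 0.855 / 0.8 = 1.07 |

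The estimator itself is unbiased. The exaggeration comes from the gate.

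**Reading 2: the gate is within-arm pre-post improvement, with no treatment effect and no time trend.**

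For selection of the top fraction q on a standard normal score, with z the cut point:

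- mean of those selected: λ = φ(z)/q; variance: v = 1 + zλ − λ²
- expected fall: (1 − r)λ
- SD of change: √[(1 − r)²v + 1 − r²]
- noncentrality of the paired t-test: fall/SD × √30, on 29 degrees of freedom

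For q = 0.15, z = 1.036, λ = 1.554 and v = 0.195. For q = 0.30, z = 0.524, λ = 1.159 and v = 0.265.

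| q | r | Fall (SD) | SD of change | Noncentrality | Gate opens |
|---|---|---|---|---|---|
| 0.15 | 0.6 | 0.622 | 0.819 | 4.16 | 98% |
| 0.15 | 0.7 | 0.466 | 0.726 | 3.52 | 92% |
| 0.30 | 0.6 | 0.464 | 0.826 | 3.07 | 84% |
| 0.30 | 0.7 | 0.348 | 0.731 | 2.61 | 71% |

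At r = 0.8 the range is 52% to 77%, and at r = 0.9 it is 29% to 47%.

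This reading adds little exaggeration. In a separate simulation with entry at EPDS 14 or more (assumed population mean/SD 7/5, 8/5 and 9/5.5; r of 0.5 to 0.7), gating on the intervention arm shifted the between-arm difference by only about 0.01 to 0.2 EPDS points. The fault here is that the gate is uninformative, not that it inflates the estimate.

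**The case against.** The strongest reply is that the trial's main question is not gated at all. One of the change-score test, mixed ANOVA or ANCOVA is run whatever the paired tests show, and the sentence naming the essential question belongs to one of those unconditional analyses. Model 1, being group alone on change scores, has the same point estimate as the change-score comparison, and pre and post means are reported for both arms in any case. All of this stands.

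A reader might infer three stronger things that the text does not support:

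- **That the essential question is answered only after a significant result.** It is not; the three analyses carry no condition.
- **That the trial's published effect is biased upward.** Only the supplementary adjusted estimate is selected, and an unselected group comparison always stands beside it.
- **That a null trial would contain no adjustment of any kind.** If ANCOVA is chosen, the baseline score is adjusted for regardless. What would be missing is adjustment for imbalanced baseline factors.

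It is also fair that the two harms belong to alternative readings and cannot both be charged, and that the protocol does not offer the paired tests as evidence of efficacy. The regression-to-the-mean calculation assumes selection on a single scale. Mothers may enter on either EPDS or GAD-7 and are then assessed with the MINI, so the fall on each scale may be smaller. R-DAS is not an entry score, so the argument does not reach it.

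None of this removes the conflict between an unconditional promise to adjust and a conditional model that delivers it.

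**Conclusion.** The concern holds for the covariate-adjusted estimate. The plan promises it without condition and then makes it depend on an undefined significance result.

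Under a between-arm gate it would be absent in about 79%, 52% and 14% of trials at true d of 0.3, 0.5 and 0.8, and would average about 2.0, 1.4 and 1.07 times the truth when present. The loss is therefore serious for small to moderate effects and slight for large ones. Under a within-arm gate it would usually be reported at correlations of 0.6 to 0.7, on a criterion that says little about treatment for EPDS and GAD-7.

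The opening rates and ratios rest on the assumed effects, covariate correlation, selection fractions and pre-post correlations. The conflict in the text does not.

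**What to change.** In Analytic Methods, delete the opening condition of the regression paragraph ("Should the results indicate that there has been significant improvement at post-testing, one should also evaluate for any differences in the change of scores"). State instead that Models 1 and 2 will be run and reported, with bootstrap confidence intervals, for EPDS, GAD-7 and R-DAS whatever the earlier tests show. Report within-arm changes descriptively and do not use them to decide whether any between-group model is run.

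The cost is an edited sentence and one extra model per outcome that is always run. No data collection or sample size changes.

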#### Measures

All Pre-Measures will take place before the interventions for all participants prior to randomisation into intervention and control groups respectively.

Post measures will take place after the intervention which is of 19 weeks duration.

We will evaluate such an outcome with the following pre-post measures.

Pre Measures:

(i)EDPS for prenatal and postnatal depression of the parents

The Edinburgh Postnatal Depression Scale (EPDS) is one of the most widely used screening instruments for assessing symptoms of perinatal depression and anxiety both in a clinical setting and also for research purposes (Gibson et al, 2009; Kozinsky and Dudas, 2015).

It is a 10-item scale written in the past tense with four possible responses graded according to the severity and duration of the symptom during the previous seven days. The scoring method is simple: 0 for absence of the symptom; 3 for maximum severity and duration; 1 and 2 which were intermediate. The total score ranged from 0 to 30.

This self-reporting instrument was originally developed in the U.K. Cox et al, (1987) specifically for childbearing women. The popularity of this brief instrument reflects the original British validation study

in which nine out of ten women who were diagnosed by a psychiatrist as being depressed after giving birth were correctly identified in a blinded comparison with scores above a cut-off on the EPDS. The psychometric properties of the EPDS in primary health care were: 86 % sensitivity (correctly identifying true cases), 78 % specificity (correctly identifying people without the condition) and 73 % positive predictive value (proportion of respondents scoring positive in the test who had a mental disorder diagnosed by clinical interview) (Cox et al, 1987).

The EPDS was acceptable to women, took only 5 minutes to complete and was rapidly scored. It screens only for depression and those who score below the cut-off should not be assumed to have no psychiatric disorder. A higher response rate (95%) is obtained when the EPDS is sent by post and careful follow-up of non-responders is carried out (Cox et al, 1993).

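### The follow-up bootstrap regression models change scores and plans no baseline outcome score in either model, so its adjusted effect is less precise than it could be and still moves with chance baseline imbalance

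*Protocol*

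**What the plan says.** All of the following is in the protocol.

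- **Timing (Measures).** The outcome scales are taken before allocation: "All Pre-Measures will take place before the interventions for all participants prior to randomisation".
- **Candidate main tests (Analytic Methods, options 1 to 3).** Option 1 compares change scores between arms, option 2 is a mixed ANOVA whose interaction test is equivalent to option 1, and option 3 is "Analysis of covariance (ANCOVA) of post-intervention scores with baseline score as the covariate". Of option 3 the protocol says: "ANCOVA adjusts the pre-test scores, increasing the power to determine whether or not there has been a treatment effect". The choice among the three is left open.
- **Follow-up regression (Analytic Methods, after option 3).** It is conditional: "Should the results indicate that there has been significant improvement at post-testing". Its purpose is to "evaluate for any differences in the change of scores between the two groups through stepwise linear regression", with 5000 bootstrap replications. The models are set out as "Groups alone will be included in Model 1, and any confounds that differed across the two groups at baseline will be included in Model 2". The stated reason for having both is to set an unadjusted effect size beside an adjusted one.
- **What counts as a confound (Analytic Methods, baseline comparison).** "Any baseline demographic factor that differed between the two groups at p < 0.10 will be included as a potentially confounding variable". This rule governs the later models of the intervention effect, and it names no outcome scale.

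**The concern.** Subtracting the baseline score is not the same as adjusting for it. A change score fixes the slope of post on pre at 1. In most symptom scales the slope is below 1, so the arm that happens to start higher on EPDS or GAD-7 tends to show the larger fall through regression to the mean. A regression that includes the baseline score estimates the slope and removes this.

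As planned, neither model does so. Model 2 is presented as the adjusted result, yet it omits the covariate most likely to predict the outcome. If option 3 is the main test, the follow-up regression returns to a less precise estimator and may give a different effect for the same scale. Choosing ANCOVA as the main test would not cure this, because the regression is specified separately.

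**Working it through.** **Inputs.** From the protocol: 60 mothers, 30 per arm; significance at p < 0.05. Not given: the pre-post correlation ρ, the SDs and the effect size. No figure of the plan's own exists to reproduce. I assume ρ = 0.3, 0.5 and 0.7 and a two-sided test.

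**Step 1. General formula.** Before any screening, let pre and post have SD 1 and correlation ρ, so the slope of post on pre is ρ. Let V be the variance of the baseline score among enrolled mothers. Selection on baseline leaves the slope and the residual variance 1 − ρ² unchanged. Per mother:
- change score: (1 − ρ)²V + (1 − ρ²)
- baseline score in the model: 1 − ρ²
- proportion of variance saved: (1 − ρ)²V / [(1 − ρ)²V + 1 − ρ²]

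**Step 2. No narrowing of the baseline range (V = 1; R-DAS has no entry cut-off).** The saving reduces to (1 − ρ)/2.
- ρ = 0.3: 0.7/2 = 35%
- ρ = 0.5: 0.5/2 = 25%
- ρ = 0.7: 0.3/2 = 15%

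Sixty mothers with the baseline score in the model are then worth 60/0.65 ≈ 92, 60/0.75 = 80 and 60/0.85 ≈ 71 without it.

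**Step 3. Entry by cut-off (EPDS and GAD-7).** Trial Design asks for scores above the cut-off on both scales; inclusion criterion 3 asks for either. I assume a cut-off 1 SD above the mean and an EPDS–GAD-7 correlation of 0.7. Simulation under these assumptions gives a baseline SD among entrants of about 0.50 (both scales) or 0.69 (either scale), so V ≈ 0.25 or 0.476.

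| ρ | Both scales | Either scale |
|---|---|---|
| 0.3 | 0.1225/(0.1225 + 0.91) ≈ 12% | 0.233/(0.233 + 0.91) ≈ 20% |
| 0.5 | 0.0625/(0.0625 + 0.75) ≈ 8% | 0.119/(0.119 + 0.75) ≈ 14% |
| 0.7 | 0.0225/(0.0225 + 0.51) ≈ 4% | 0.043/(0.043 + 0.51) ≈ 8% |

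At ρ = 0.5, 60 mothers are worth about 65 to 69, not 80.

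**Step 4. Small-sample cost.** Estimating the slope inflates the adjusted variance by about 1 + 1/(2 × 30 − 4) = 1.018. In simulation with V = 1 the variance ratios (change over adjusted) were 1.48, 1.31 and 1.17, against 1.54, 1.33 and 1.18 from the formula. The 4% saving in Step 3 becomes 1 − 0.96 × 1.018 ≈ 2%.

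**Step 5. Sensitivity to imbalance.** The chance difference in baseline means has SE √(2/30) = 0.258 baseline SDs. It exceeds 0.25 SD in 33% of randomisations. The change-score estimate moves by (1 − ρ) times the imbalance, in the opposite direction. A 1-SE imbalance at ρ = 0.5 shifts it by 0.5 × 0.258 = 0.13 SD when V = 1. For the screened scales the shift is 0.5 × 0.50 × 0.258 ≈ 0.06 to 0.5 × 0.69 × 0.258 ≈ 0.09 of the unscreened SD. In simulation with V = 1 the slope of the change-score estimate on imbalance was −0.69, −0.50 and −0.31 for ρ = 0.3, 0.5 and 0.7; with the baseline score in the model it was within 0.012 of zero.

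**Step 6. Type I error.** In 40,000 simulated null trials at ρ = 0.5 and V = 1, the change-score test rejected in 5.1% overall. Among trials with imbalance above 1 SE (about 32%) it rejected in 9.1%. In the remainder it must reject in about (5.1 − 0.32 × 9.1)/0.68 ≈ 3.2%.

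**The case against.** **The plan already has a baseline-adjusted analysis.** True. A reader might infer that Models 1 and 2 give the trial's only covariate-adjusted effect. They do not: option 3 adjusts for the baseline score. What is particular to Model 2 is adjustment for confounders beyond that score. The point is limited to the follow-up regression.

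**The change-score test is valid.** Also true. A reader might infer from the 9% in Step 6 that the test is biased or anti-conservative. That figure is conditional on having selected the imbalanced trials. Over repeated randomisation the estimate is unbiased and the error rate is about 5%.

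**The gain is smaller than the textbook formula suggests.** This stands for EPDS and GAD-7. Entry by cut-off narrows the baseline range while post scores can spread, so about half or more of the equal-SD saving disappears. The direction remains.

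**It is only a triggered, secondary step.** This stands too. The precision gain should not be read as a gain in the trial's power to detect a benefit.

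**The word for confounds in Model 2 could admit a baseline score.** On a wide reading, yes, but the defining rule earlier in the section names demographic factors. Even on the wide reading, the score would enter only after an imbalance test, not by plan.

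**Putting the baseline score in Model 1 would remove the unadjusted contrast that the protocol wants.** This is right, and the fix respects it.

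**Conclusion.** The point holds as a loss of precision and a sensitivity to the realised imbalance in the estimate labelled adjusted. It is not a validity defect. The text fixes both models, and neither contains the baseline score of the outcome by plan. The same section says that using that score raises power.

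The variance saving forgone is 15–35% where pre and post SDs are equal, which is plausible for R-DAS. It is roughly 4–20% for EPDS and GAD-7, depending on the correlation and on whether entry needs one scale or both. These ranges rest on an assumed ρ of 0.3 to 0.7, bivariate normal scores, a cut-off 1 SD above the mean and an EPDS–GAD-7 correlation of 0.7. They are before the small-sample cost of about 2%, which leaves little gain at the bottom of the range. The change is worth making because it is nearly free and puts the adjusted estimate on the same footing as option 3.

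**What to change.** In Analytic Methods, in the paragraph on the bootstrap regression, state that Model 2 always includes the baseline score of the outcome being analysed (EPDS, GAD-7 or R-DAS), whatever the observed imbalance and without being subject to stepwise removal. Keep Model 1 as group alone, so that the unadjusted contrast survives. Alternatively, add an intermediate model of group plus baseline score; its group coefficient equals that of option 3, because with the baseline score in the model the change score and the post score give the same group effect. Keep the 5000 replications.

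The cost is one sentence and one degree of freedom in each model that gains the score. The baseline scores are already planned for collection.

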# **Trial Design**

A two-group design is appropriate:

Those mothers who score above the cut-off point on the EPDS and the GAD 7 with depression or anxiety will receive psychiatric assessment plus medication (if needed) plus a monthly phone call by a midwife, plus 12 sessions of systemic therapy in the **Intervention Group** 

And a psychiatric assessment plus medication (if needed) plus a monthly phone call by a midwife in the **Control Group** 

The outcomes

AN Mothers who score above the cut-off point on the EPDS and the GAD 7

with anxiety and depression in the Intervention Group will have a better outcome reflected through:

- (i) a lower and statistically significant score on the EPDS and GAD7 when compared to those in the control group
- (ii) a higher statistically significant score on the Dyadic Adjustment Scale Revised (R-DAS) when compared to those in the Control Group

The allocation ratio is intended to be as follows:

**60 mothers**; (30 ANmothers will be in the intervention group, whereas **30**ANmothers will be in the control group)

During the screening process, AN mothers who score above the cutoff point in the EPDS and the GAD7 will be put in one cluster. The randomisation into the intervention and the control group will take place through the process described below.

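### No primary outcome and no success rule: EPDS, GAD-7 and R-DAS rank equally at an unadjusted 0.05, so what counts as a better outcome could be settled after the results

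*Protocol*

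**What the plan says.** In the Protocol, Trial Design, the hypothesis is that mothers "with anxiety and depression in the Intervention Group will have a better outcome reflected through" two items. Item (i) is "a lower and statistically significant score on the EPDS and GAD7 when compared to those in the control group". Item (ii) is "a higher statistically significant score on the Dyadic Adjustment Scale Revised (R-DAS) when compared to those in the Control Group". The section does not call either item, or any scale, primary.

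Analytic Methods treats the three scales alike. It offers "three adequate ways to analyse a numerical outcome (GAD-7, EPDS and R-DAS"), adding that "the best approach will be chosen accordingly". For the first of these methods the criterion is only this: "The overall test is statistically significant if it yields a sufficiently small p-value". The one numerical threshold for treatment effects comes at the end of the regression paragraph: "Results will be determined to be statistically significant if p values were <0.05". The text contains no ranking of outcomes, no adjustment for several outcomes, and no statement of which result would count as success. It also does not say whether the tests are one-sided or two-sided.

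**The concern.** The hypothesis can be read in at least two ways. A better outcome might be shown by any one of the three scales, or only by all of them together. Under the first reading, three tests at 0.05 each carry more than twice the false-positive risk of one test. Under the second, error is controlled, but the trial needs three significant results from 30 mothers per arm.

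Because the protocol does not choose, the choice could follow the data. A single significant scale could be presented as showing that the therapy works, or as falling short, and the protocol could be cited for either.

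A multiplicity procedure may be left to a statistical analysis plan. The primary outcome and the meaning of success are design decisions. The protocol takes them up itself, by stating the hypothesis and a flat 0.05, and leaves them unresolved.

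**Working it through.** **Inputs from the Protocol.** Three outcomes (Trial Design; Analytic Methods). Threshold 0.05 (Analytic Methods). 30 mothers per arm (Trial Design; Trial Flow Chart).

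**Assumptions, not in the Protocol.** Two-sided tests, pairwise correlations of 0.3, 0.5 and 0.7 between the test statistics, and 80% power for each outcome alone. The Protocol gives no family-wise error rate and no power calculation, so there is no figure of its own to reproduce.

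**1. Any one outcome suffices, false difference in either direction.** Independent outcomes: 1 − (1 − 0.05)³ = 1 − 0.8574 = 14.3%. Correlated outcomes: share of 2,000,000 trivariate normal draws with at least one |z| > 1.96.

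**2. Any one suffices, counting only false results favouring the therapy.** Independent outcomes: 1 − (1 − 0.025)³ = 7.3%, against 2.5% for one outcome.

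**3. All three required.** Independent outcomes, no effect on any: 0.05³ = 0.01%. In general the error cannot exceed 5%.

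**4. Holm.** The smallest p-value is compared with 0.05/3 = 0.0167. Independent outcomes, no effect on any: 1 − (1 − 0.0167)³ = 4.9%.

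**5. Joint power if all three are required.** 80% power at two-sided 0.05 means an expected z of 1.96 + 0.84 = 2.80. Independent outcomes: 0.8³ = 51%. Correlated outcomes: share of draws with all three z > 1.96.

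| Pairwise correlation | Any, either direction | Any, favouring therapy | All three, either direction | Holm, either direction | Joint power, all three |
|---|---|---|---|---|---|
| 0 | 14.3% | 7.3% | 0.01% | 4.9% | 51% |
| 0.3 | 13.6% | 6.8% | 0.09% | 4.8% | 57% |
| 0.5 | 12.5% | 6.3% | 0.3% | 4.4% | 61% |
| 0.7 | 10.9% | 5.5% | 0.9% | 3.9% | 66% |

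The error columns assume no effect on any outcome. At a correlation of 0.8 the either-direction rate for any outcome falls to 9.9%.

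**6. Check at the trial's size.** With correlations of 0.6 between EPDS and GAD-7 and 0.3 between each of them and R-DAS, the normal calculation gives 13.0%. Simulated change-score tests at 30 per arm also give 13.0%, with 5.0% per single test.

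**7. One-sided variant.** If each test is one-sided at 0.05, the chance of at least one false result favouring the therapy runs from 14.3% (independent) to 10.3% (correlation 0.7), against 5%.

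**8. A mixed reading.** Suppose success means both scales in item (i), or item (ii) alone. Independent outcomes: 1 − (1 − 0.05²)(1 − 0.05) = 1 − 0.9975 × 0.95 = 5.2%. With equal correlations of 0.7 it is 5.8%.

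**The case against.** The strongest objection is that the hypothesis does not invite a claim on any one scale. Item (i) joins EPDS and GAD-7 with a conjunction, and items (i) and (ii) may be meant together. If all three are required, there is no inflation. Under the mixed reading in step 8 there is almost none. This stands in part: the inflated rates depend on the any-one reading, and the documents do not establish it. They do not exclude it either. The two items are listed as ways in which benefit shows itself, not as a joint condition, and Analytic Methods tests each scale separately.

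A reader might infer that the trial carries an 11% to 14% chance of falsely declaring the therapy better. The documents do not support that. The range counts differences in either direction, whereas the hypothesis is directional. With two-sided tests, false results favouring the therapy run at 5.5% to 7.3% against 2.5%. The higher range would fit that event only with one-sided tests at 0.05, which the protocol does not specify.

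Three further points stand as limits:

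- The correlations are assumptions. Only 14.3% needs no chosen correlation, and it takes the outcomes as independent.
- The sentence with the 0.05 threshold closes the paragraph on follow-up regression. Its wording covers results in general and no other figure is given for treatment effects, but its reach is a reading.
- The protocol undertakes to compare all the measures, so non-significant scales should also be visible in a report. That limits concealment but does not say which result decides the trial.

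The open choice among three analysis methods is a separate matter and is not counted in these figures.

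**Conclusion.** The point holds as a missing primary outcome and a missing success rule. It does not show that the trial has an inflated error rate under every reading.

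If any one scale may be claimed, the risk of a false significant result is about two to three times that of a single test, in either direction or in favour of the therapy. If all three are required, error is safe, but roughly a third or more of trials with a true effect on every scale would fail (joint power 57% to 66%). That figure rests on the assumed 80% per outcome and the assumed correlations.

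Because the text bears both readings, the main conclusion has no meaning fixed in advance. This must be settled before outcome data are seen; it cannot be repaired credibly afterwards.

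**What to change.** State in the outcomes part of Trial Design, and again in Analytic Methods, that the between-group tests of EPDS, GAD-7 and R-DAS after the 19-week intervention period are judged by Holm at a family-wise two-sided 0.05. Add that the therapy is called effective only on outcomes significant under that rule. When no outcome is affected, this holds the error at about 4% to 5% for the correlations shown.

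Alternatively, name one primary outcome, justify it, and treat the other two as secondary. The justification matters because a mother can enter on either EPDS or GAD-7 (Participants, Inclusion Criteria). Neither scale is the obvious choice for everyone enrolled, and placing one first in a fixed sequence would block a claim on the other whenever the first fails.

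The change is to wording only: no added mothers, visits or data. The cost is a stricter threshold for individual claims. An outcome with 80% power at 0.05 has about 66% at Holm's first step, 0.0167 (2.80 − 2.39 = 0.41, and the normal probability below 0.41 is 0.66). Later steps are less strict.
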